12.8. Safety Analyses

All safety analyses for the double-blind period will be conducted based on the Safety Analysis Set.

Safety data will include AEs, physical examination results, vital signs, ECG results, and clinical laboratory measurements. Observed data will be listed by patient and summarized using descriptive statistics by treatment group for the double-blind period.

12.8.1. Physical Examination and Vital Signs

The number and percentage of patients with physical examination abnormalities at each visit will be summarized and presented for each body system. A listing of abnormalities will also be provided.

The presence and staging of edema will be summarized by frequency counts and percentages based on semi-quantitative (0, 1+, 2+, 3+, 4+) evaluation of physical examination findings. A shift table indicating changes in edema from baseline to each post-baseline visit will be provided.

Vital signs data will be summarized as changes from baseline and will be classified as low, normal, or high based on reference ranges prespecified in the SAP. Vital sign abnormalities for each treatment will be summarized using shift tables.

12.8.2. Clinical Laboratory Tests

Clinical and laboratory parameters will be measured at baseline and post-baseline visits. Each continuous laboratory variable will be summarized as changes from baseline by treatment group.

Laboratory data will also be classified as low, normal, or high relative to the parameter's reference range. Laboratory abnormalities for each treatment will also be summarized using shift tables.

12.8.3. Adverse Events

Adverse events will be mapped to preferred term and body system using MedDRA. Adverse events that begin after the first administration of study medication, or existing AEs that worsen after the first dose of study medication are considered TEAEs. The number and percentage of patients reporting TEAEs will be summarized for each treatment group by MedDRA system organ class and preferred term, then by severity, and by relationship to study medication. Drug-related TEAEs will be considered those to be at least possibly related to study medication based on the Investigator's assessment. The number and percentage of patients reporting serious AEs or AEOIs, and the number and percentage of patients reporting AEs leading to treatment

discontinuation will also be summarized for each treatment group by MedDRA system organ class and preferred term.

12.8.4. Other Safety Assessments

Electrocardiogram results will be presented descriptively by treatment group and visit and will also be listed.

12.9. Other Analyses

12.9.1. Prior Medications, Concomitant Medications, and Concomitant Medical Procedures

Concomitant medications will be coded using the WHO-DD, and concomitant medical procedures will be coded using MedDRA. The incidence of prior medications, concomitant medications, and concomitant medical procedures will be summarized using frequency and percentage for the double-blind period and separately for the open-label extension.

The use of diuretics required for controlling urine volume, edema, and blood pressure will be summarized separately. Specifically, the number of patients requiring an increase, decrease, or no change in the number of diuretics used from baseline will be analyzed. Prior to analysis, a defined list of medications based on coded terms will be developed to identify appropriate diuretics for this analysis. For the double-blind period, this review and identification of diuretics will be conducted prior to unblinding.

All concomitant medications and medical procedures will be listed for individual patients by treatment group; this listing will include the indication for use, start/stop date, dose/units, frequency, and route of administration.

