4.1. Summary of Potential Risks

The potential risks for patients treated with sparsentan are a consequence of its dual antagonist properties of both angiotensin and endothelin receptor blockade. Due to its ARB properties, sparsentan imparts a potential risk of acute kidney injury (AKI) due to reductions in intracapillary glomerular pressure, and a risk of hyperkalemia due to lower glomerular filtration rate (GFR) and aldosterone inhibition. In addition, syncope has been identified as a risk due to sparsentan's antihypertensive properties. These risks are accentuated in patients with reduced kidney function, volume depletion, and those being treated with non-steroidal anti-inflammatory drugs (NSAIDs). Studies have also shown that treatment with ERAs is associated with increased rates of edema and congestive heart failure (CHF) in patients with diabetic nephropathy (Mann 2010).

Selective and nonselective endothelin ET_A /endothelin receptor subtype B (ET_B) receptor antagonists are expected to cause fetal harm (harm to a developing embryo) if given to pregnant women. Similarly, ARBs have been shown to reduce fetal renal function and increase fetal and neonatal morbidity and death during the second and third trimesters of pregnancy. However, a recently completed, thorough, scientific evidence-based review of all available toxicology data evaluating the risk of genotoxic and teratogenic effects of sparsentan in male patients and their female partners indicates that, similar to marketed ERAs and ARBs, the requirement for contraception in male study patients is not warranted.

Because of these potential risks, sparsentan should be used with caution in patients with CKD Stages 3 and 4 and with extreme caution in patients with CKD Stage 5 and patients at risk of AKI. Moreover, sparsentan should be avoided in patients with CHF Stages 2 through 4, and in women who are or may become pregnant or who are breastfeeding.

For details regarding all nonclinical and clinical data on sparsentan, as well as warnings, precautions, and contraindications, the Investigator should refer to the appropriate section of the [Investigator's Brochure](#).

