15.2.2. Recommendations for Management of Hyperkalemia

Serum potassium checks should be completed at each visit for clinical evidence of electrolyte imbalance. If a patient has a serum potassium value >5.5 mmol/L (5.5 mEq/L) at any time during the study, the following steps are recommended:

[figure not shown]
1. If the serum potassium value is ≥ 6.5 mmol/L, emergency management should be implemented based on the site policies and Investigator's decision.
2. If the serum potassium value is >5.5 and <6.5 mmol/L (6.5 mEq/L), rule out measurement errors or likely reasons for the increase (eg, sample hemolysis, metabolic acidosis, discontinuation of diuretic intake by the patient/lack of compliance, diet transgression).
 - a. If the causes listed above are ruled out and the patient is not receiving a diuretic, it is recommended to start a diuretic (if the patient's volume status and blood pressure permit). The choice of a thiazide or a loop diuretic is at the discretion of the Investigator. Assess the patient's tolerability and measure their blood pressure, eGFR, sodium, and potassium within 1 week after starting the diuretic.
 - b. If the causes listed above are ruled out and the patient is already receiving a diuretic, increase the dose of the diuretic by 50% (if the patient's volume status and blood pressure permit). Assess the patient's tolerability and measure their blood pressure, eGFR, sodium, and potassium within 1 week after increasing the dose. Consider correction of metabolic acidosis, if relevant.
3. In both scenarios 2a and 2b, adjust the dose of diuretic accordingly after 1 week. If the patient's serum potassium value is still >5.5 mmol/L, reinforce diet counseling/restrictions, rule out other potential causes of hyperkalemia, and consider increasing the diuretic dose. If, after an additional week, the serum potassium value is still >5.5 mmol/L, reduce the dose of study medication by 50%. For long-term prevention of hyperkalemia, consider treatment with patiromer or sodium zirconium cyclosilicate.
4. If hyperkalemia persists or recurs, study medication must be discontinued permanently.

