5.4. Changes from Planned Protocol Analyses

The analyses specified in this SAP are consistent with DUPLEX Protocol Amendment 6 with the following exception.

The primary statistical evaluation of the surrogate endpoint, FPPE, will be performed using the Interim Analysis Set (IAS) rather than the subset of patients in the FAS who are scheduled to have completed their Week 36 visit per Section 12.11 of the protocol. Statistical evaluation of FPPE using the subset of patients in the FAS who are scheduled to have completed their Week 36 visit will be performed as a sensitivity analysis.

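### Diuretic change is classified by the number of drugs, so a dose-only increase is tabulated as no change, and the SAP omits the table without saying so

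*Protocol*

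**What the plan says.** Protocol 12.9.1 sets the diuretic summary apart from the general medication tables and states its purpose: "The use of diuretics required for controlling urine volume, edema, and blood pressure will be summarized separately". The classification rule follows: "Specifically, the number of patients requiring an increase, decrease, or no change in the number of diuretics used from baseline will be analyzed". No category refers to dose. The same section plans a by-patient listing of all concomitant medications, and "this listing will include the indication for use, start/stop date, dose/units, frequency, and route of administration".

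Diuretic changes also appear in the hyperkalemia guidance, Protocol 15.2.2. The trigger is potassium: "If a patient has a serum potassium value >5.5 mmol/L (5.5 mEq/L) at any time during the study, the following steps are recommended". For a patient not on a diuretic, "it is recommended to start a diuretic". Where "the patient is already receiving a diuretic, increase the dose of the diuretic by 50" percent is the instruction. Both steps are conditional on volume status and blood pressure.

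SAP 10.3 summarizes medications by ATC level and preferred name and defines a new concomitant medication by its start date. The post-baseline diuretic subgroup in SAP 8.3 is limited to patients with no baseline use. Neither section contains the increase, decrease or no-change table. SAP 5.4 states: "The analyses specified in this SAP are consistent with DUPLEX Protocol Amendment 6 with the following exception". That exception concerns the analysis set for the surrogate endpoint.

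**The concern.** A count of drugs cannot register a higher dose of the same drug or a one-for-one switch. Two patients with the same clinical need are then classified differently according to whether they were on a diuretic at baseline: one starts a drug and is an increase, the other has the dose raised and is no change.

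Diuretic use is worth measuring well here. Protocol 4.1 names edema and heart failure among the risks seen with endothelin receptor antagonists, and diuretic use helps in reading edema grades, since edema controlled by a higher dose may show no worse grade at a visit. The trial already treats another co-medication more fully: for immunosuppressants, Protocol 6.1.1.3 and SAP 8.8.4 count initiation or intensification. Diuretics get only a count, and the SAP drops even that.

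**Working it through.** **No planned figure to reproduce.** Neither document states a rate, test or power for the diuretic summary. The check is mainly textual.

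**Step 1: apply the rule in 12.9.1 to typical patients.**

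| Baseline | During treatment | Number of diuretics | Tabulated as |
|---|---|---|---|
| None | Starts one | 0 to 1 | Increase |
| One | Second one added | 1 to 2 | Increase |
| One | Same drug, higher dose | 1 to 1 | No change |
| One | Replaced by another | 1 to 1 | No change |

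Under 15.2.2, the start step falls in the first row and the dose step in the third.

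**Step 2: look for a repair in the SAP.** Section 10.3 works from drug class, name and start date, and section 8.3 covers new users only. The documents do not say whether a dose change opens a new medication record. If it does, the start-date rule in 10.3 could count it as a new medication; if not, it is invisible there too.

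**Step 3: is the omission undeclared?** The SAP claims consistency with Amendment 6, whose text is not supplied; the protocol supplied is Amendment 9. The history in Protocol 15.4 lists no change to 12.9.1 in Amendments 7 to 9 beyond minor edits, so the table was probably already in Amendment 6. That is an inference.

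**Step 4: illustrate the size on assumed rates.** True intensification is assumed to be 20% on irbesartan and 30% on sparsentan. Let s be the share of intensified patients whose change is by dose alone.

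Counted rate = true rate × (1 − s).

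Equal share in both arms:

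| s | Irbesartan | Sparsentan | Difference | Risk ratio |
|---|---|---|---|---|
| 0 | 20% | 30% | 10 points | 1.50 |
| 25% | 0.20 × 0.75 = 15% | 0.30 × 0.75 = 22.5% | 7.5 points | 1.50 |
| 50% | 0.20 × 0.50 = 10% | 0.30 × 0.50 = 15% | 5 points | 1.50 |

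Both rates and their difference shrink by the factor (1 − s); the ratio does not move.

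Unequal shares:

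| s irbesartan | s sparsentan | Counted rates | Difference | Risk ratio |
|---|---|---|---|---|
| 50% | 25% | 10% vs 22.5% | 12.5 points | 2.25 |
| 25% | 50% | 15% vs 15% | 0 points | 1.00 |
| 20% | 60% | 16% vs 12% | −4 points | 0.75 |

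Against the assumed truth of 10 points and 1.50, the count can overstate, erase or reverse the contrast. No power is given because neither document specifies a test for this table.

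**The case against.** The strongest reply is that this is a supporting table and that fluid retention is covered elsewhere. That stands. SAP 10.1.2 summarizes fluid-retention adverse events, including related and serious ones, on study and on treatment. SAP 10.7.1 tabulates the shift in edema to the worst value, unscheduled assessments included. Body weight is a safety endpoint in Protocol 6.1.2. None of these uses the diuretic count, and Protocol 10.1 allows worsening of a baseline condition to be recorded as an adverse event. A reader might infer that edema managed by dose would go unseen in every analysis; the documents do not support that.

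A reader might also take the dose step in 15.2.2 as proof that a response to edema is being missed. It is not: the trigger is potassium above 5.5 mmol/L, and hyperkalemia is not among the purposes named in 12.9.1. No passage directs a diuretic dose increase for edema. The step shows only that dose increases are foreseen in this trial and that the count would not register them. It also means that adding dose increases without regard to indication would mix potassium-driven changes into a summary meant for urine volume, edema and blood pressure.

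Finally, the by-patient listing holds dose and indication. That preserves the information, but a listing is not a comparison between arms.

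**Conclusion.** The point holds in a limited form. The rule in 12.9.1 tabulates dose-only intensification as no change, nothing in the SAP repairs it, and the SAP leaves out the table without listing that among its departures. The number of patients with intensified diuretic use is understated if even one patient has a dose-only increase.

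The stronger reading, that the fluid-retention signal of sparsentan is understated, is not established. The absolute difference shrinks predictably only when the dose-only share is equal in the two arms, and the risk ratio is then unchanged. With unequal shares the error can go either way. All the rates above are assumptions chosen to show the mechanism. The conclusion about the SAP rests on the protocol history being complete for 12.9.1. This is a cheap improvement to a supporting safety table; it does not threaten the trial's main safety conclusions.

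**What to change.** In Protocol 12.9.1:

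- Define an increase as an added diuretic or a higher total daily dose of the same diuretic, relative to the baseline regimen. Define a decrease in the mirror-image way, and state how a patient meeting both definitions is shown.
- Report one-for-one switches as their own category, so that no dose equivalence between agents has to be assumed.
- Tabulate by treatment arm and by recorded indication, with urine volume, edema and blood pressure kept apart from hyperkalemia.
- Keep the count-only classification as an additional row.

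Carry the table into SAP 10.3, with a rule for how a dose change in the medication record is handled. If the table is to be left out, declare that in SAP 5.4. Settle the definition together with the list of diuretic terms, which 12.9.1 already requires before unblinding for the double-blind period.

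The cost is wording in two sections and modest programming. Dose, frequency, dates and indication are already planned for the listing, so no new data are needed. The limitation is reliance on how completely dose and indication are recorded; a row for missing indication would make that visible.

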12.9.2. Pharmacokinetics

Trough plasma study medication levels will be summarized using descriptive statistics.

12.10. Other Statistical Issues

12.10.1. Significance Levels

Unless otherwise specified, all tests will be 2-tailed, using a 0.05 level of significance. All CIs will be 2-sided 95% CIs.

12.10.2. Multiple Comparisons/Multiplicity

To control the overall type I error for this study when conducting significance tests for the primary and secondary efficacy endpoints, a hierarchical (gate-keeping) testing procedure will be used.

The surrogate efficacy endpoint (UP/C response at Week 36) will first be tested at the interim analysis at 2-sided $\alpha = 0.05$. If the test is not significant, hypothesis testing stops. If the test is significant, then the following country-specific hierarchical testing will be performed.

For non-US countries, the hierarchy for the hypothesis testing will be as follows, if the test of the surrogate efficacy endpoint (UP/C response at Week 36) is significant:

1. test the primary efficacy endpoint (eGFR chronic slope over 2 years) at the final analysis at 2-sided $\alpha = 0.05$. If the test is not significant, hypothesis testing stops. If the test is significant,
2. test the 3 secondary endpoints using a Bonferroni-Holm procedure to control for family-wise error rate at 2-sided $\alpha = 0.05$.

For the US, the hierarchy for the hypothesis testing will be as follows, if the test of the surrogate efficacy endpoint (UP/C response at Week 36) is significant:

1. test the primary efficacy endpoint (eGFR total slope over 2 years) at the final analysis at 2-sided $\alpha = 0.05$. If the test is not significant, hypothesis testing stops. If the test is significant,
2. test the efficacy endpoint of eGFR chronic slope over 2 years at the final analysis at 2-sided $\alpha = 0.05$. If the test is not significant, hypothesis testing stops. If the test is significant,
3. test the efficacy endpoint of change in eGFR from baseline of the double-blind period to 4 weeks post-cessation of randomized treatment at Week 112 at the final analysis at 2-sided $\alpha = 0.05$.

12.10.3. Missing Data

Patients who discontinue will not be replaced. To the extent possible, attempts will be made to minimize the amount of missing data through measures planned in the study conduct. However, if missing data are present, they will be handled as follows:

- Continuous endpoints analyzed via mixed-effects models (including the primary efficacy endpoint): Only available data will be analyzed, using the mixed-effects model with random slope and intercepts and the MMRM approaches described throughout [Section 12.7.1](#). These models implicitly adjust for missing data through a variance covariance structure.
- UP/C response: Missing data at specific visits will be imputed using an MI procedure. Sensitivity analyses will also be performed on observed cases (ie, no imputation) and at Week 36 only imputing missing data as non-responders.

12.11. Interim Analysis

An unblinded interim analysis will be performed after 36 weeks following randomization of at least 190 patients (approximately 95 patients per treatment group) to determine whether the surrogate endpoint (the proportion of patients achieving a UP/C ≤ 1.5 g/g [170 mg/mmol] and a $>40\%$ reduction from baseline in UP/C) is statistically significant. The statistical evaluation will be performed on the subset of patients in the FAS who are scheduled to have completed their Week 36 visit, using a generalized linear model with logit link function, at a significance level of $\alpha = 0.05$. The interim analysis will be conducted by an independent statistical team, and the study team will remain blinded to the interim data (see [Section 8.6](#)). No unblinded individual patient data will be published. Processes to ensure that the blind is appropriately preserved will be detailed and documented prior to unblinding for the interim analysis.

12.12. Analyses for the Open-Label Extension

Analysis of endpoints for the open-label extension will be performed using the methods described in the sections above as appropriate.

Efficacy and safety endpoints for the open-label extension will be summarized using descriptive statistics and presented overall and by original randomized treatment based on the OLEFAS. Analyses using baselines other than Week 112 (eg, prior to first dose of study medication in the double-blind period) may be explored; details will be provided in the SAP.

13. SPECIAL REQUIREMENTS AND PROCEDURES

This protocol was designed and will be conducted, recorded, and reported in compliance with the ICH Harmonised Tripartite Guidelines for Good Clinical Practice, 1996; ICH Guidelines for Safety Data Management, 1994; the US Code of Federal Regulations (CFR 21 Parts 50, 56, and 312); and the EU Clinical Trials Directive, 2001/20/EC. The protocol meets legal and regulatory requirements according to the country of conduct.

13.1. Institutional and Ethics Review

This protocol and associated ICF, patient information sheet, any information provided to the patient, the [Investigator's Brochure](#), and any proposed advertising material will be submitted to an appropriate IRB/IEC, applicable regulatory authorities, and host institution(s) for written approval (where applicable). These documents will also be submitted to, and approved by, the above parties for all amendments to the original approved documents (where applicable) prior to implementation. Documentation of any applicable approval(s) and the approved ICF and assent form (if applicable) will be received by the Sponsor or its designee prior to enrollment of patients and release of study medication.

13.2. Data Monitoring Committee

During the double-blind period, the study will employ an independent DMC that may include nephrology, internal medicine, statistician(s), and/or pharmacovigilance physicians. The DMC members will not be involved in the study as Investigators or consultants. The DMC will have study conduct oversight as defined by the DMC charter. All members will have considerable experience with clinical study conduct and DMCs. Any candidate found to have a financial, intellectual, or personal conflict of interest, or whose name is listed on the FDA debarment list, will not be offered membership. Conflicts of interest will be assessed regularly, and if members are found to have a new conflict of interest they will be replaced.

The DMC will meet approximately biannually at scheduled meetings but may agree to adjust meeting frequency based upon actual and projected data availability. In addition, ad hoc meetings may be convened, as appropriate, to review safety data. Based on review of available data, the DMC will advise the Sponsor on the validity and scientific merit of continuing the study. Adjustments to or stopping of the protocol defined doses may be considered based on DMC evaluation of safety and tolerability data.

Written minutes of both open and closed DMC sessions will be prepared. The minutes of closed sessions will be made available to the appointed Sponsor representatives only after the database is locked and all data are unblinded.

The DMC may request unblinded individual patient data as appropriate. Data reviewed during the meetings will include, at a minimum, disposition, demographics, exposure, clinical laboratory results, MedDRA-coded AEs, and AEs leading to early withdrawal of study medication. At each meeting, detailed narratives of interval SAEs (including events resulting in death) are reviewed by the DMC in addition to a cumulative list of all SAEs.

All Investigators and responsible IRBs/IECs will be informed of any decisions made by the Sponsor based on recommendations from the DMC relating to patient safety that alter the

conduct of this study. The Investigators will inform patients of such actions, and the protocol and ICF will be revised, as appropriate.

